By my signature, I agree to personally supervise the conduct of this study and to ensure its conduct in compliance with the protocol, informed consent, IRB/HRPO procedures, the Declaration of Helsinki, ICH Good Clinical Practices guidelines, and the applicable parts of the United States Code of Federal Regulations or local regulations governing the conduct of clinical studies.

Primary Objective

To determine the clinical response rate of patients with Stage I-III B (cT1-3, N0-1, M0) rectal cancer being treated with sequential short course radiotherapy followed by 8 cycles of multi-drug chemotherapy.

Secondary Objectives:

1. To obtain prospective patient reported outcomes from an organ preservation approach towards early stage rectal cancer
2. To determine the incidence of any grade ≥ 3 toxicity during treatment
3. To determine the incidence of post chemoradiotherapy grade ≥ 3 toxicity at 1 year
4. Determine quality of anorectal function at 1 year using the FACT-C questionnaire

Table of Contents

SCHEMA.....	5
1 BACKGROUND.....	8
2 OBJECTIVES.....	9
2.1 Primary Objective	9
2.2 Secondary Objectives.....	9
3 ELIGIBILITY CRITERIA	10
3.1 Inclusion Criteria.....	10
3.2 Exclusion Criteria.....	10
3.3 Inclusion of Women and Minorities.....	11
4 Patient Registration.....	11
4.1 Confirmation of Patient Eligibility.....	11
4.2 Patient Registration in the Siteman Cancer Center OnCore Database.....	11
4.3 Assignment of UPN	12
5 EVALUATION STUDIES.....	12
5.1 Pre-treatment	12
5.2 During Radiotherapy and Chemotherapy.....	12
5.3 Completion of Chemotherapy/Post-Treatment Evaluation	13
5.4 Follow-up	13
6 RADIATION THERAPY GUIDELINES.....	13
6.1 Dose, Fractionation	13
6.2 Treatment Planning Procedures	14
6.3 Simulation Procedures/Patient Positioning	14
6.4 Clinical Target Volume (CTV) and Planning Target Volume (PTV) Definitions.....	14
6.5 Normal Tissue Contours.....	15
7 CHEMOTHERAPY GUIDELINES.....	15
7.1 Chemotherapy Schedule and Doses	15
7.2 Agent Administration.....	15
7.3 Supportive Care Recommendations	16
8 DOSE DELAYS/DOSE MODIFICATIONS.....	16
8.1 Dose Levels.....	17
8.2 Dose Modifications for Toxicity Related to FOLFOX-6.....	18
8.3 Dose Modifications for Neurologic Toxicity (Paresthesia or Dysesthesia) Related to Oxaliplatin.....	19
9 ADVERSE EVENT REPORTING	19
9.1 Definitions.....	19
9.2 Reporting to the Human Research Protection Office (HRPO) at Washington University 21	

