7 CHEMOTHERAPY GUIDELINES

7.1 Chemotherapy Schedule and Doses

Chemotherapy should begin 2 to 4 weeks after completion of radiotherapy and will consist of 5FU/leucovorin/oxaliplatin every other week for 8 courses (16 weeks). Alternatively, capecitabine/oxaliplatin (CAPE PO 1000 mg/m² BID days 1-14 Q21 days, oxaliplatin IV 130 mg/m² IV Q21 days on day 1) x 5 cycles over 15 weeks may be administered instead of FOLFOX. A maximum (total) delay of treatment of 4 weeks is allowed per protocol due to factors/AEs listed in this section. Cumulative delays in excess of 4 weeks will need to be discussed with the Principal Investigator. Such cases will need to be individualized depending on the clinical scenario.

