8.1 Dose Levels

Folfox	Starting Dose	Dose Level -1	Dose Level -2	Dose Level -3
Oxaliplatin	85 mg/m ²	65 mg/m ²	50 mg/m ²	40 mg/m ²
Bolus 5-FU	400 mg/m ²	300 mg/m ²	200 mg/m ²	100 mg/m ²
Infusion 5-FU	2400 mg/m ²	1920 mg/m ²	1600 mg/m ²	1360 mg/m ²
Leucovorin	400 mg/m ²	400 mg/m ²	400 mg/m ²	400 mg/m ²

CapeOx	Starting Dose	Dose Level -1	Dose Level -2	Dose Level -3
Capecitabine	1000 mg/m ²	800 mg/m ²	600 mg/m ²	540 mg/m ²
Oxaliplatin	130 mg/m ²	104 mg/m ²	78 mg/m ²	70 mg/m ²

*Rounding capecitabine to nearest full tablet dose is acceptable (i.e. Dose 1900 mg rounded to 2000 mg (4x 500 mg tablets) daily).

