8.2 Dose Modifications for Toxicity Related to FOLFOX and CapeOx

The provided dose modifications are strongly recommended. However, out of consideration of unforeseen clinical scenarios, dose modifications during FOLFOX chemotherapy are ultimately at the discretion of the primary treating provider. The use of 5-FU bolus is at the discretion of the treating physician. Modifications should be reported to the research coordinator. Refer to table 8.2 and 8.3 for guidance regarding suggested dose reductions and treatment delays, consistent with best oncologic practices.

Toxicity NCI Grade (Value)	Worst interval toxicity	Day of treatment
Neutropenia (ANC)		
Grade 1 (ANC < LLN – 1500/mm ³)	Maintain dose level	If ANC < 1000 on day of treatment, hold and check weekly until ≥ 1000 mm ³ . Then treat based on interval toxicity. If ANC < 1000 after 4 weeks, discontinue therapy.
Grade 2 (ANC < 1499 – 1000/mm ³)		
Grade 3 (ANC < 999 – 500/mm ³)	Reduce 1 dose level	
Grade 4 (ANC < 500/mm ³)		
Thrombocytopenia		
Grade 1 (PLT < LLN – 75,000/mm ³)	Maintain dose level	If PLT < 75,000 on day of treatment, hold and check weekly until ≥ 75,000 mm ³ . Then treat based on interval toxicity. If PLT < 75,000 after 4 weeks, discontinue therapy.
Grade 2 (PLT 74,999 – 50,000/mm ³)		
Grade 3 (PLT 49,999 – 25,000/mm ³)	Reduce 1 dose level	
Grade 4 (PLT < 25,000/mm ³)		
Diarrhea		
Grade 1	Maintain dose level	Hold chemotherapy if any grade of diarrhea above grade 1 is present with the patient not taking antidiarrheal agents within 24 hours of treatment. Reduce 5-FU and oxaliplatin 1 dose level upon resolution of diarrhea. If diarrhea has not resolved within 4 weeks of scheduled treatment day, discontinue therapy.
Grade 2		
Grade 3		
Grade 4		
Other nonhematologic toxicities (except neurologic, alopecia, anorexia, nausea/vomiting if can be controlled by antiemetics)		
Grade 1	Maintain dose level	Maintain dose level
Grade 2		
Grade 3	Reduce 1 dose level	Hold until resolved to grade ≤1. Reduce 5-FU and oxaliplatin 1 dose level
Grade 4		

8.3 Dose Modifications for Neurologic Toxicity (Paresthesia or Dysesthesia) Related to Oxaliplatin

Grade	Duration of Toxicity		
	1 – 7 Days	> 7 Days	Persistent Between Doses
Grade 1 Short duration that resolves and does not interfere with function	No change	No change	No change
Grade 2 Interfering with function, but not activities of daily living (ADL)	No change	No change	Reduce oxaliplatin 1 dose level

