10.2.7 Administration

Fluorouracil will be given as a 400 mg/m² IV bolus injection followed by 2400 mg/m² continuous IV infusion over 46 hours.

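### The diarrhea restart rule in Section 8.2 covers CapeOx but reduces only 5-FU and oxaliplatin, so read literally capecitabine restarts unreduced, most clearly after grade 2 diarrhea

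*Combined protocol and SAP*

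**What the plan says.** Section 7.1 allows capecitabine plus oxaliplatin in place of FOLFOX, with capecitabine given as "CAPE PO 1000 mg/m² BID days 1-14 Q21 days", for five cycles. Section 8.1 has a separate CapeOx dose-level table: capecitabine 1000, 800, 600 and 540 mg/m², and oxaliplatin 130, 104, 78 and 70 mg/m². The heading of Section 8.2 names both regimens.

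In the diarrhea row of the 8.2 table, the day-of-treatment cell reads "Hold chemotherapy if any grade of diarrhea above grade 1 is present with the patient not taking antidiarrheal agents within 24 hours of treatment". The restart instruction follows: "Reduce 5-FU and oxaliplatin 1 dose level upon resolution of diarrhea". The matching cell for other nonhematologic toxicity at grades 3 and 4 names the same two drugs: "Hold until resolved to grade ≤1. Reduce 5-FU and oxaliplatin 1 dose level".

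The text above the table describes the modifications as strongly recommended and as suggested guidance. It leaves the final decision to the treating provider, but words that clause for FOLFOX only.

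**The concern.** A dosing rule that applies to two regimens names the fluoropyrimidine of only one. A CapeOx patient takes no 5-FU, so as written the cell reduces oxaliplatin and gives no instruction for capecitabine. For the same toxicity under the same cell, the fluoropyrimidine comes down in one regimen and, on a literal reading, stays at full dose in the other.

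This is a patient-safety matter. Grade 3 or higher toxicity during treatment is also a secondary objective, which is a further reason for dose rules that are equally clear in both regimens. The protocol provides for secondary sites, whose staff may have little beyond the written table to go on.

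**Working it through.** **Does another section supply the missing rule?**

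- Section 8.1 lists 5-FU (bolus and infusion) only under FOLFOX, and capecitabine only under CapeOx. Its one remark on capecitabine dosing concerns tablets: "Rounding capecitabine to nearest full tablet dose is acceptable".
- Section 10.2.7 describes fluorouracil as an intravenous drug: "Fluorouracil will be given as a 400 mg/m² IV bolus injection followed by 2400 mg/m² continuous IV infusion over 46 hours". Section 10 has no capecitabine entry.
- Reading one dose level as a move of the whole regimen is not secure, because the cell names the drugs it applies to. Section 8.3 shows that the protocol names a single drug when it means that drug alone: for neuropathy, "Reduce oxaliplatin 1 dose level".
- The table of contents still lists Section 8.2 as "Dose Modifications for Toxicity Related to FOLFOX-6". This fits a heading later widened to CapeOx without the cells being widened, but it does not prove that history.

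No section equates 5-FU with capecitabine or gives a separate capecitabine rule for diarrhea.

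**Where in the table is the gap certain?**

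| Row | Interval-toxicity column | Day-of-treatment column | Capecitabine covered? |
|---|---|---|---|
| Neutropenia, thrombocytopenia | Generic one-level reduction from grade 3 | Hold, then treat by interval toxicity | Yes, by the generic wording |
| Diarrhea | Only an instruction to maintain dose is visible | Hold above grade 1, then reduce 5-FU and oxaliplatin | Not at grade 2; uncertain at grades 3-4 |
| Other nonhematologic | Generic one-level reduction from grade 3 | Hold, then reduce 5-FU and oxaliplatin | Largely, by the generic interval entry |

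The table was read from PDF, so a generic reduction for grade 3 and 4 diarrhea may have been lost. In the other rows that entry starts at grade 3, so a lost entry on the same pattern would still leave grade 2 uncovered.

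**Size of the difference.** All inputs are the Section 8.1 dose levels and the Section 7.1 schedule, for a patient at starting dose and for the first course after the hold. The plan states no figure of its own to reproduce.

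Capecitabine per course = dose × 2 per day × 14 days:

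- literal reading: 1000 × 2 × 14 = 28,000 mg/m²
- level -1: 800 × 2 × 14 = 22,400 mg/m²
- difference: 28,000 − 22,400 = 5,600 mg/m²; ratio 28,000 / 22,400 = 1.25

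Oxaliplatin in CapeOx, under either reading: 104 / 130 = 0.80, a 20% reduction.

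5-FU in FOLFOX per cycle = bolus + infusion:

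- starting dose: 400 + 2400 = 2,800 mg/m²
- level -1: 300 + 1920 = 2,220 mg/m²
- reduction: 1 − 2,220 / 2,800 = 20.7%
- without the optional bolus: 1 − 1920 / 2400 = 20.0%

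| Fluoropyrimidine after a diarrhea hold | Reduction |
|---|---|
| FOLFOX, 5-FU | 20.7% (20.0% without bolus) |
| CapeOx, cell read literally | 1 − 1000 / 1000 = 0% |
| CapeOx, level -1 applied | 1 − 800 / 1000 = 20% |

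**The case against.** The best reply is that the cell is silent on capecitabine and does not say to leave it unchanged. Telling a CapeOx patient's clinician to reduce 5-FU is an instruction that cannot be carried out. The natural response, under a heading that names both regimens and beside a table of capecitabine levels, is to reduce the fluoropyrimidine in use.

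Other safeguards also apply. The hold covers all chemotherapy, so capecitabine stops too. Restart waits for the diarrhea to resolve, and treatment ends if it has not done so within four weeks. A medical oncology physician or nurse examines the patient at each cycle. The table is suggested guidance. The unreduced dose is the protocol's own starting dose, and full capecitabine with reduced oxaliplatin is not a forbidden pair, since Section 8.3 can produce it.

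Most of this stands, and it limits the weight of the point. The likely intent is indeed to reduce both drugs, and many clinicians would do so. It does not remove the defect. Restarting after resolution applies equally to FOLFOX, where the table still calls for a lower 5-FU dose. Guidance on grade 2 diarrhea helps a CapeOx patient only if it names the drug being taken. The explicit discretion clause does not settle the matter either, because it refers to FOLFOX alone.

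**Conclusion.** The concern holds. Followed as written, the diarrhea cell restarts a CapeOx patient from starting dose with capecitabine 25% above its level -1 dose, while it reduces 5-FU by about 21% in FOLFOX. This is certain as a reading of the text for grade 2 diarrhea. For grades 3 and 4 it depends on whether an interval entry is missing from the extracted table, and for other nonhematologic toxicity the generic entry already largely closes the gap.

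The figures assume a patient at starting dose and a literal reading. The documents do not give the number of CapeOx patients or of diarrhea holds, so no expected number affected can be stated. This is a safety correction to wording that should be made. It does not touch the sample size, the interim rule or the primary endpoint.

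**What to change.** In the day-of-treatment cells for diarrhea and for other nonhematologic toxicity, write: *Reduce 5-FU or capecitabine, and oxaliplatin, 1 dose level*. In the discretion sentence above the table, refer to FOLFOX or CapeOx chemotherapy.

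A CapeOx patient at starting dose would then restart at capecitabine 800 mg/m² twice daily with oxaliplatin 104 mg/m², which appears to match the intent. The cost is a few words in two cells and one sentence at the next amendment, with no added visits, staff or patients.

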9 ADVERSE EVENT REPORTING

The entities providing oversight of safety and compliance with the protocol require reporting as outline below.

The Washington University Human Research Protection Office (HRPO) requires that all events meeting the definition of unanticipated problem or serious noncompliance be reported as outlined in Section 9.2.

9.1 Definitions

9.1.1 Adverse Events (AEs)

Definition: any unfavorable medical occurrence in a human subject including any abnormal sign, symptom, or disease.

Grading: the descriptions and grading scales found in the revised NCI Common Terminology Criteria for Adverse Events (CTCAE) version 4.0 will be utilized for all toxicity reporting. A copy of the CTCAE version 4.0 can be downloaded from the CTEP website.

Attribution (relatedness), Expectedness, and Seriousness: the definitions for the terms listed that should be used are those provided by the Department of Health and Human Services' Office for Human Research Protections (OHRP). A copy of this guidance can be found on OHRP's website:

<http://www.hhs.gov/ohrp/policy/AdvEvtGuid.html>

9.1.2 Serious Adverse Event (SAE)

Definition: any adverse drug experience occurring at any dose that results in any of the following outcomes:

- Death
- A life-threatening adverse drug experience
- Inpatient hospitalization or prolongation of existing hospitalization
- A persistent or significant disability/incapacity (i.e., a substantial disruption of a person's ability to conduct normal life functions)
- A congenital anomaly/birth defect
- Any other experience which, based upon appropriate medical judgment, may jeopardize the subject and may require medical or surgical intervention to prevent one of the outcomes listed above

9.1.3 Unexpected Adverse Experience

Definition: any adverse drug experience, the specificity or severity of which is not consistent with the current investigator brochure (or risk information, if an IB is not required or available).

9.1.4 Life-Threatening Adverse Experience

Definition: any adverse drug experience that places the subject (in the view of the investigator) at immediate risk of death from the reaction as it occurred, i.e., it does not include a reaction that, had it occurred in a more severe form, might have caused death.

9.1.5 Unanticipated Problems

Definition:

- unexpected (in terms of nature, severity, or frequency) given (a) the research procedures that are described in the protocol-related documents, such as the IRB-approved research protocol and informed consent document; and (b) the characteristics of the subject population being studied;
- related or possibly related to participation in the research (in this guidance document, possibly related means there is a reasonable possibility that the incident, experience, or outcome may have been caused by the procedures involved in the research); and
- suggests that the research places subjects or others at a greater risk of harm

(including physical, psychological, economic, or social harm) than was previously known or recognized.

9.1.6 Noncompliance

Definition: failure to follow any applicable regulation or institutional policies that govern human subjects research or failure to follow the determinations of the IRB. Noncompliance may occur due to lack of knowledge or due to deliberate choice to ignore regulations, institutional policies, or determinations of the IRB.

9.1.7 Serious Noncompliance

Definition: noncompliance that materially increases risks, that results in substantial harm to subjects or others, or that materially compromises the rights or welfare of participants.

9.1.8 Protocol Exceptions

Definition: A planned deviation from the approved protocol that are under the research team's control. Exceptions apply only to a single participant or a singular situation.

Local IRB pre-approval of all protocol exceptions must be obtained prior to the event. For secondary sites, the Washington University PI will issue approval of the exception, but it must also be submitted to the local IRB with documentation of approval forwarded to Washington University. Washington University IRB approval is not required for protocol exceptions occurring at secondary sites.

9.2 Reporting to the Human Research Protection Office (HRPO) at Washington University

The PI is required to promptly notify the IRB of the following events:

- Any unanticipated problems involving risks to participants or others which occur at WU, any BJH or SLCH institution, or that impacts participants or the conduct of the study.
- Noncompliance with federal regulations or the requirements or determinations of the IRB.
- Receipt of new information that may impact the willingness of participants to participate or continue participation in the research study.

These events must be reported to the IRB within **10 working days** of the occurrence of the event or notification to the PI of the event. The death of a research participant that qualifies as a reportable event should be reported within **1 working day** of the occurrence of the

event or notification to the PI of the event.

9.3 Reporting to the Quality Assurance and Safety Monitoring Committee (QASMC) at Washington University

The PI is required to notify the QASMC of any unanticipated problem occurring at WU or any BJH or SLCH institution that has been reported to and acknowledged by HRPO as reportable. (Unanticipated problems reported to HRPO and withdrawn during the review process need not be reported to QASMC.)

QASMC must be notified within **10 days** of receipt of IRB acknowledgment via email to a QASMC auditor.

9.4 Reporting Requirements for Secondary Sites

The research team at each secondary site is required to promptly notify the Washington University PI and research coordinator of all reportable events (as described in Section 9.2) within **1 working day** of the occurrence of the event or notification of the secondary site's PI of the event. This notification may take place via email if there is not yet enough information for a formal written report (using either an FDA MedWatch form if required or an institutional SAE reporting form if not). A formal written report must be sent to the Washington University PI and research coordinator within **10 working days** of the occurrence of the event or notification of the secondary site's PI of the event. The death of a research participant that qualifies as a reportable event should be reported within **1 working day** of the occurrence of the event or notification of the secondary site's PI of the event.

The research team at a secondary site is responsible for following its site's guidelines for reporting applicable events to its site's IRB according to its own institutional guidelines.

9.5 Reporting to Secondary Sites

The Washington University PI (or designee) will notify the research team at each secondary site of all reportable events that have occurred at other sites within **10 working days** of the occurrence of the event or notification of the PI of the event. This includes events that take place both at Washington University and at other secondary sites, if applicable.

9.6 Timeframe for Reporting Required Events

All Grade 3 and above adverse events should be collected until 1 year post start of radiation therapy on case report forms and reported to the QASMC as part of the DSM Report as applicable.

10 PHARMACEUTICAL INFORMATION

FOLFOX is a standard of care, FDA-approved regimen for the treatment of rectal cancer, and treatment will be provided and administered according to standard of care guidelines. More detailed information can be found in the products' package inserts.

10.1 Leucovorin

10.1.1 Mechanism of action

Leucovorin is a tetrahydrofolate acid derivative that acts as a biochemical cofactor for carbon transfer reactions in the synthesis of purines and pyrimidines. Leucovorin does not require the enzyme dihydrofolate reductase for conversion to tetrahydrofolic acid. Leucovorin potentiates the effects of fluorinated pyrimidines like 5-FU. Leucovorin increases the folate pool, increasing the binding of folate cofactor and active metabolites of 5-FU.

10.1.2 Pharmacodynamics

Leucovorin is well absorbed after oral administration and is readily converted to 5-methyltetrahydrofolate after administration. Peak serum concentrations occur 1.7 to 2.5 hours after an oral dose. Leucovorin is excreted in the urine as metabolites and has a half-life of approximately 2-6 hours.

10.1.3 Availability

Leucovorin calcium is commercially available in: 50 mg, 100 mg, 350 mg vials for reconstitution.

10.1.4 Supplier(s)

Leucovorin is commercially available and will not be provided by this study.

10.1.5 Storage and Stability

Intact vials should be stored at room temperature and protected from light. Solutions reconstituted with Bacteriostatic Water for Injection (BWI) are stable for at least 7 days at room temperature.

10.1.6 Administration

Leucovorin may be reconstituted with BWI or with sterile water. Solutions should be further diluted in D5W, 0.9% NaCl or Ringers solution for infusion over two hours.

Leucovorin will be administered as a 400 mg/m² IV infusion over 2 hours. It may

be given either concurrent with (via a separate infusion line) or following oxaliplatin and immediately before fluorouracil.

10.2 5-Fluorouracil (5-FU)

10.2.1 Mechanism of Action

Fluorouracil, $C_4H_3FN_2O_2$, a pyrimidine antagonist, is an antimetabolite antineoplastic agent. Although the precise mechanisms of action of fluorouracil have not been fully elucidated, the main mechanism is thought to be the binding of the deoxyribonucleotide of the drug (FdUMP) and the folate cofactor, N5-10-methylenetetrahydrofolate, to thymidylate synthase (TS) to form a covalently bound ternary complex, which inhibits the formation of thymidylate from uracil, thereby interfering with DNA synthesis. In addition, FUTP can be incorporated into RNA in place of uridine triphosphate (UTP), producing a fraudulent RNA and interfering with RNA processing and protein synthesis.

